4.10. Safety Evaluation

All safety summaries and analyses will be based upon the Safety Set as defined in Section 4.5.

Risk difference and corresponding 95% CI in the crude incidence rates between each active treatment group (or total ISIS 678354) and pooled placebo group in selected safety endpoint will be provided. The crude incidence rate (or percentage) is defined as the number of patients who experienced at least one event times 100 divided by the total number of patients. The 95% CI of risk difference in crude incidence rate will be estimated using the Miettinen-Nurminen (MN) method.

4.10.1. Extent of Exposure

The exposure to treatment will be presented in terms of the duration of exposure (in days), number of doses administered, and amount of Study Drug received for each patient. The duration of exposure will be calculated as the last dose date minus the first dose date plus 28 days (one dose interval) for each patient. Treatment duration, number of doses, and amount of Study Drug received will be summarized by treatment group.

Compliance with Study Drug administration will be summarized by descriptive statistics by treatment group.

The evaluation of compliance of ISIS 678354 will be done using the following formula:

Actual total dose injected (mg) *100/Expected total dose (mg) to be administered.

The evaluation of compliance of placebo will be done using the following formula:

Actual total volume injected (mL) *100/Expected total volume (mL) to be administered.

Patients in Cohort A will receive 50 mg of ISIS 678354 once every 4 weeks or matching volume of placebo (0.5 mL) Weeks 1-49 of the Treatment Period. Patients in Cohort B will receive 80 mg ISIS 678354 once every 4 weeks or matching volume of placebo (0.8 mL) Weeks 1-49 of the Treatment Period.

For early withdrawals/terminations, the total dose injected will be calculated for the period up to their withdrawal/termination.

The following summaries will be provided:

- A summary of the duration, number of doses administered and the total amount of study drug by treatment group
- A summary of percent compliance by treatment group.
- Number of patients with dose interruption due to AE and number of patients with study drug reduced due to AE.
- A summary of number of days of dose interruption.

The following listings will be provided:

- A by-subject listing of administration of study drug
- A by-subject listing of treatment compliance

4.10.2. Adverse Events

All adverse events will be coded by the MedDRA coding system. The final version used will be designated in the clinical study report.

The following imputation rules will be applied to impute start dates under conservative principles:

- If year, month and day are all missing then assign the date of first dose of Study Drug.
- If month and day are missing and year is:
 - the same as the year of the first dose of Study Drug then assign the month-day of first Study Drug
 - o earlier than the year of the first dose of Study Drug then assign December 31
 - \circ after the year of the first dose of Study Drug then assign January 1
- If only day is missing and month-year is:
 - the same as the month-year of the first dose of Study Drug then assign the day of first Study Drug
 - $\circ~$ earlier than the month-year of the first dose of Study Drug then assign the last day of the month
 - $\circ~$ after the month-year of the first dose of Study Drug then assign the first day of the month

Imputation will be performed for the end date only if the day or month is missing (i.e., year is present) for a resolved AE as follows:

- If month and day are missing and year is:
 - the same as the year of the last dose of Study Drug then assign the month-day of the last dose of Study Drug
 - o otherwise, assign December 31
- If only day is missing then assign the last day of the month

If the imputed start date is later than the imputed end date then set the imputed start date to the imputed end date.

An adverse event will be regarded as treatment emergent if it is present prior to receiving the first dose of study drug and subsequently worsens, or is not present prior to receiving the first dose of study drug but subsequently appears.

In addition, if the severity of an AE changes during the study, a separate AE will be recorded for each severity on the AE CRF. The "first" and "second" AE records will be identified based on the AE start date. AE start date of the second record will be the AE stop date of first record. These linked events should be compared pairwise. Consider the following two cases, where the AE severity (mild/moderate/severe) and seriousness (Yes/No) between the two records in a pair are compared.

Case 1: The first AE record in the pair occurs before the first dosing, and the second AE record occurs after the first dosing.

If the AE severity or seriousness of the second record is worse than that of the first record, then only the second AE is deemed as a TEAE. Otherwise, neither record is considered as TEAE.

Case 2: Both AE records in the pair occur after first dosing.

The worst AE is considered as a TEAE.

- The frequency of patients with any incidence of AEs and the number events will be summarized by MedDRA preferred term and system organ class for:
- Any TEAE
- TEAEs potentially related to Study Drug. Related is defined as "Related", "Possible", or missing relationship to Study Drug
- Any treatment-emergent adverse event by severity. At each level of patient summarization, a patient is classified according to the worst reported severity if the patient reported one or more events. Adverse events with missing severity will be categorized as "Missing" for this summary.
- TEAEs potentially related to Study Drug by severity
- TEAEs leading to treatment discontinuation
- TEAEs leading to death
- Serious TEAEs
- Serious TEAEs potentially related to Study Drug
- TEAE with an incidence rate > 5% in any treatment groups
- Non-serious TEAE with an incidence rate > 5% in any treatment groups

Adverse event summaries will be presented alphabetically by SOC and preferred term (PT) and by descending frequency. An overview of AEs will be provided for all TEAes. AEs that lead to treatment discontinuation, and AEs that lead to death will be listed.

In addition, a summary of adjudicated AEs will be provided for pancreatitis and MACE separately. Adjudicated events will also be listed.

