4.10.4. Other Events of Interest

4.10.4.1. Local Cutaneous Reactions at the Injection Site

Local cutaneous reaction at injection site (LCRIS) is defined as (A) moderate or severe adverse events with the preferred terms (PTs) including Injection site erythema, Injection site swelling, Injection site pruritus, or Injection site pain that started on the day of injection, persisted for at least two days (i.e., event onset date on the day of injection and resolution date not on the day of injection or the day after injection) or ongoing; or (B) any AE at the Study Drug injection site, regardless of severity, that leads to discontinuation of study drug, where AE at the Study Drug injection site is the principal reason for discontinuation. LCRIS will be summarized using the MedDRA coding system, by PT and by treatment group. Patients with moderate, severe and any LCRIS will also be summarized. Discontinuations due to AE at the injection site will be summarized separately.

Percentage of injections leading to LCRIS will be summarized by PT and overall using the descriptive statistics. Additionally, percentage of injections leading to events will be summarized by moderate, severe severity and overall discontinuation of Study Drug due to AE at injection site.

Percentage of injections leading to LCRIS will be calculated as follows for each patient: (A/B)*100, where A = number of injections with a LCRIS, and B = total number of injections. Doses that are split across multiple injections are counted as a single injection.

The duration to resolution of a LCRIS will be summarized descriptively by treatment group and total ISIS 678354 treated. If there are multiple LCRIS related to an injection and no overlap between events, the duration will be calculated as the sum of the duration of all LCRIS that are related to the injection. If there are overlaps, the duration will be calculated using the earliest start date and latest stop date of all LCRIS that are related to the injection. For unresolved LCRIS with missing stop date, the last participation date will be used in the calculation.

In addition, for patients who experienced LCRIS, time to onset of the first event, the number of injections prior to the first LCRIS will also be summarized descriptively by treatment group and total ISIS 678354 treated.

LCRIS will also be listed.

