4.10.4.3. Flu-like Reactions

Flu-like reactions (FLR) will be evaluated using the following 2 definitions:

Definition 1 (FLR 1): defined as adverse events with PTs including Influenza like illness, Pyrexia, Feeling hot, Body temperature increased, Chills, Myalgia, or Arthralgia, starting on the day of injection or next day.

ISIS 678354-CS3

Definition 2 (FLR 2): defined as adverse events with PTs including either (A) Influenza like illness or (B) Pyrexia or Feeling hot or Body temperature increased, plus at least two of the following symptoms with the PTs: Chills, Myalgia, or Arthralgia, starting on day of injection or the next day.

Flu-like reactions will also be summarized using the MedDRA coding system, by preferred term and by treatment group.

Percentage of injections leading to flu-like reactions will be summarized by treatment group using the descriptive statistics.

Percentage of the injections leading to flu-like reactions will be calculated as follows for each patient: (A/B)*100, where A = number of injections leading to flu-like reactions, and B = total number of injections.

For the subset of patients experiencing FLR(s), the time to onset of first FLR will be summarized using descriptive statistics.

Flu-like reactions will also be listed.

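### Imputed adverse-event start dates also decide which events count as flu-like reactions or LCRIS part A, so those tables should be shown with and without them

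*Combined protocol and SAP*

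**What the plan says.** SAP 4.10.2 gives start-date rules described as conservative:

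- Everything missing: "If year, month and day are all missing then assign the date of first dose of Study Drug".
- Month and day missing, matching year: "the same as the year of the first dose of Study Drug then assign the month-day of first Study Drug". A later year gives 1 January, an earlier one 31 December.
- Day missing, matching month: "the same as the month-year of the first dose of Study Drug then assign the day of first Study Drug".
- Day missing, later month: "after the month-year of the first dose of Study Drug then assign the first day of the month".
- Day missing, earlier month: "earlier than the month-year of the first dose of Study Drug then assign the last day of the month".

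For the end date of a resolved event the rule is "If only day is missing then assign the last day of the month".

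Two later definitions use the exact onset day. SAP 4.10.4.3 defines FLR 1 by a list of preferred terms ending "Chills, Myalgia, or Arthralgia, starting on the day of injection or next day", and FLR 2 has the same two-day window. Part A of LCRIS in SAP 4.10.4.1 covers moderate or severe injection-site erythema, swelling, pruritus or pain "that started on the day of injection, persisted for at least two days", or ongoing. Both definitions feed incidence, percentage of injections affected and time to first onset. Section 4.10.4.1 says what to do when the stop date of an unresolved LCRIS is missing, but neither section says whether an imputed start date may satisfy the onset condition.

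**The concern.** Dating an uncertain event early is cautious when the question is whether it began after the first dose. It is not cautious when the question is whether it began on an injection day. There the same rule errs both ways. It assigns events to the first injection whether or not they started then, and it moves later reactions to the first of the month, which is rarely an injection day.

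Protocol 9.4.2 starts adverse-event recording at consent. A fever during screening, in the same calendar month as the first dose and with its day missing, would thus be dated Day 1 and meet FLR 1.

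At stake is how faithfully the safety tables describe injection-related reactions. With small arms, one or two events can alter that picture.

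**Working it through.** The SAP states no figure for this point, so there is none to reproduce. All results are per incomplete start date, because the share of incomplete dates is not given.

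**Inputs.** Date rules: SAP 4.10.2. Onset windows: injection day for LCRIS part A (SAP 4.10.4.1); injection day or the day after for FLR (SAP 4.10.4.3). Dosing every 28 days over Weeks 1 to 49: (49 − 1)/4 + 1 = 13 doses, matching protocol 8.1. Arm sizes 21, 22 and 23: results summary at the front of the combined document. Assumption: first-dose dates run over every day from 1 December 2020 to 30 September 2022.

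**1. Day missing, first-dose month.** All such events go to Day 1. Suppose both the first dose and the event are spread evenly over a 30-day month, giving 30 × 30 = 900 pairs. The event falls on the dose day or the next day in 30 + 29 = 59 pairs, 59/900 = 6.6%. It precedes the dose in 30 × 29/2 = 435 pairs, 435/900 = 48.3%.

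**2. Day missing, true reaction on the injection day of doses 2 to 13.** By hand, let the injection fall on day d of a later month. The imputed first of the month is an injection day if d = 1, or if d = 29 (the previous injection was 28 days earlier). It is the day after an injection if d = 28. With 365/12 = 30.4 days per month:

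- LCRIS part A window: 2/30.4 = 6.6%
- FLR window: 3/30.4 = 9.9%

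Applying the rules to every date in the assumed range, which also handles short months and second doses in the first-dose month, gives 6.7% and 10.0%. About 93% and 90% respectively lose the onset condition. A reaction on Day 1 itself always keeps it.

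**3. Day missing, unrelated event spread evenly over Days 1 to 365.**

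| Onset falls on | True date | Imputed date |
|---|---|---|
| Injection day | 13/365 = 3.6% | 7.6% |
| Injection day or next day | 26/365 = 7.1% | 11.1% |
| Day 1 | 1/365 = 0.3% | 4.3% |

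**4. More of the date missing.** With month and day missing, about 53% of true reactions at doses 2 to 13 move to Day 1; about 55% still meet the LCRIS part A window and 57% the FLR window. With everything missing, all go to Day 1.

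**5. Persistence in LCRIS part A.** If the start and stop days are both missing in the first-dose month, the start becomes Day 1 and the stop becomes month-end. The two-day persistence condition is then met by imputation unless the dose fell on one of the month's last two days.

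**6. Scale per patient.** One misclassified patient moves an arm's incidence by 100/23 = 4.3 to 100/21 = 4.8 points. Protocol 2.3.4 reports Phase 2 flu-like rates of 8.9% on active drug and 8.3% on placebo. At these arm sizes that is about two patients per arm (0.089 × 22 = 2.0; 0.083 × 23 = 1.9).

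**The case against.** A reader might infer that imputation fills the tables with false Day 1 reactions and erases real ones across all injection-site outcomes. The documents do not support that.

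- The SAP's own injection site reaction (4.10.4.2) and part B of LCRIS have no onset-day condition. Imputation can touch the former's classification only through persistence.
- LCRIS part A also needs moderate or severe grade and persistence. The fever route into FLR 2 needs at least two further symptoms. A Day 1 date alone creates neither.
- An injection-site event cannot precede the first injection. A second dose falls in the first-dose month only when the first is given on about the 1st to the 3rd (about 8% of dates). Linking a day-missing injection-site event in that month to dose 1 is therefore usually right, though a delayed onset could still be misdated. The false Day 1 problem mainly concerns FLR.
- Nothing is erased from the safety record. An event that loses FLR or LCRIS status remains in the treatment-emergent tables of 4.10.2. When all parts are missing, a later reaction still counts for patient incidence, but at the wrong injection and with the wrong time to onset.
- Events are reviewed at each visit (protocol Appendix A) and omissions are queried (protocol 12.4), so incomplete dates may be few.
- Sections 4.10.4.1 and 4.10.4.3 plan no test or risk difference, and the rules apply alike in every blinded arm.

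All of this stands, and it limits the point. It does not close the gap for FLR 1, FLR 2 and LCRIS part A, where the imputed day can decide classification. The planned listings help only partly: a reaction listing built on the same derivation would omit an event that had lost its status.

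**Conclusion.** The point holds as a small, conditional flaw in descriptive safety tables. Read as written, SAP 4.10.2 lets a date chosen to settle treatment emergence also settle injection-day onset. Per day-missing date, an event in the first-dose month always goes to Day 1, and a true injection-day reaction at doses 2 to 13 keeps its onset status about 10% of the time (FLR) or 7% (LCRIS part A).

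These percentages rest on the 28-day schedule being kept, the assumed range of first-dose dates, and onset on the injection day itself. They say nothing about how many events are affected, and no statement about actual bias in this trial is justified without that count. The primary analysis, the secondary endpoints and type I error are untouched. The 7-day onset window in the hypersensitivity algorithm (SAP 4.10.4.6) shares the same dependence on onset date but was not quantified.

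**What to change.** State in SAP 4.10.2 that imputed start dates serve to assign treatment-emergent status. For FLR 1, FLR 2, LCRIS part A, percentage of injections affected and time to first onset, present results both with and without events whose start date was imputed, and give the number of such events by arm. Do the same for the 7-day hypersensitivity algorithm.

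Showing both is better than restricting the main tables to complete dates. That restriction would remove every incomplete-date event from the main FLR and LCRIS part A counts, including dose-1 reactions that the present rule keeps.

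The cost is a sentence in the SAP, a flag in the derivation and one extra display. No new data are needed. If incomplete dates are rare, the two versions will agree and the count by arm will show why.

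### SAP 4.10.2 gives conflicting TEAE flags when an adverse event with a pre-dose record has two or more post-dose severity records, because Case 2 is not limited to chains that start after first dosing

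*Combined protocol and SAP*

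**What the plan says.** SAP 4.10.2 begins with a general definition: "An adverse event will be regarded as treatment emergent if it is present prior to receiving the first dose of study drug and subsequently worsens". An event that starts only once dosing has begun also qualifies. The section then deals with events that change grade: "if the severity of an AE changes during the study, a separate AE will be recorded for each severity on the AE CRF". For the resulting records, "These linked events should be compared pairwise", and "the AE severity (mild/moderate/severe) and seriousness (Yes/No) between the two records in a pair are compared".

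Two cases follow.

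- Case 1 has the first record before first dosing and the second after it. If the second is worse in severity or seriousness, only the second is a TEAE. "Otherwise, neither record is considered as TEAE".
- The condition for the other case reads "Case 2: Both AE records in the pair occur after first dosing". The outcome is "The worst AE is considered as a TEAE".

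Case 2 contains no condition on how the chain began. The section does not say how to treat chains of three or more records, or which case prevails when one record belongs to two pairs.

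**The concern.** The general definition and Case 1 both ask whether a pre-existing event got worse. Case 2 asks only which of two post-dose records is the worse, and one of them always is. A pre-existing event with two post-dose records can therefore be flagged under Case 2 even if it never got worse.

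The flag matters because SAP 4.10.2 builds its main adverse event tables on it: any TEAE, related, by severity, serious, and incidence above 5% in any group. The event-of-interest summaries in SAP 4.10.4.4 to 4.10.4.8, with their risk differences, also rest on TEAEs. For the chains in question a programmer has to make a choice that the SAP does not record, and two programmers who both follow the text could produce different tables.

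**Working it through.** The documents state no figure for this rule, so there is none to reproduce. The check applies the two cases literally to consecutive linked records.

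**Can such chains arise?** Recording of AEs and SAEs starts at consent (Protocol 9.4.1, 9.4.2), and screening may last up to 8 weeks (Protocol 3.4.1). A condition present before consent becomes an AE only if it worsens (Protocol 9.4). Protocol 9.4.3.5 provides for a change in severity, and for moves between serious and non-serious with linked dates. A pre-dose record followed by several post-dose records is therefore possible.

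**Two records, one before and one after dosing, severity only.** There are 3 × 2 = 6 chains. Three improve, and Case 1 clears all three. There is no problem here.

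**Three records, one before and two after dosing, severity only.** There are 3 × 2 × 2 = 12 chains, since adjacent records must differ. Five never exceed the pre-dose severity, and all five receive a Case 2 flag:

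| Chain (pre-dose first) | Case 1 on records 1 and 2 | Case 2 on records 2 and 3 | Any worsening step after dosing? |
|---|---|---|---|
| severe, moderate, mild | neither is a TEAE | record 2 (moderate) is a TEAE | no |
| severe, moderate, severe | neither | record 3 | yes |
| severe, mild, moderate | neither | record 3 | yes |
| severe, mild, severe | neither | record 3 | yes |
| moderate, mild, moderate | neither | record 3 | yes |

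The direct contradiction, with one record both cleared and flagged, is in the top row. It is also the only chain of pure improvement.

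**Adding seriousness.** With 3 × 2 = 6 states there are 6 × 5 × 5 = 150 three-record chains. Ten improve steadily, never worsening on either attribute, and in all ten the middle record is cleared by Case 1 and flagged by Case 2.

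**Scale of one patient.** The results summary that precedes the protocol gives 21 patients on 50 mg, 22 on 80 mg and 23 on placebo.

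- One patient: 1/21 = 4.8%, 1/22 = 4.5%, 1/23 = 4.3%.
- Two patients: 2/21 = 9.5%, 2/22 = 9.1%, 2/23 = 8.7%.

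In each arm a term reported by one patient lies below the 5% cut and a term reported by two lies above it, so one additional patient can decide whether the term is tabulated.

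**Check of the remedy.** If each post-dose record is compared with the pre-dose record, all five chains in the table give 0 TEAEs. With several pre-dose records the comparator has to be the last one. In severe (pre-dose), mild (pre-dose), moderate (post-dose), Case 1 compares mild with moderate and flags a TEAE. Using the worst pre-dose record would remove that flag.

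**The case against.** The strongest reply is that the general definition comes first and the pairwise rule is an addition written for a first and a second record. On that reading, overlapping pairs in a longer chain were never intended, Case 1 agrees with the definition, and nothing is miscounted. This stands in part: the literal outcome is a contradiction, not a certain TEAE. It does not remove the gap. The SAP requires a record for each severity, sets no limit of two, and states no precedence.

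Three stronger readings are tempting, and the documents do not support them.

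- A reader might infer that the SAP definitely counts improvement as harm. It does so only if Case 2 is allowed to override Case 1, and an event that improves in a single step is correctly excluded.
- A reader might infer a bias against the active arms. The rule is the same in every arm, and nothing in the documents shows stepwise improvement to be more common in one of them.
- A reader might treat all five chains as plain errors. Four of them contain an on-treatment worsening step. The definition does not say against which earlier state worsening is judged, so flagging moderate, mild, moderate can be defended as conservative.

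The likely exposure is also narrow. Most pre-existing conditions are medical history, not AEs. The pure-improvement chain on severity alone needs a patient with a severe AE before dosing who is nevertheless randomized and dosed, and then two recorded improvements. A patient who already has the same term as a TEAE does not change its incidence. SAP 4.10 promises risk differences only for selected endpoints. Protocol 10.6 lists all eCRF data, so the records stay visible.

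**Conclusion.** The defect is real and minor. Where an event has a pre-dose record and at least two post-dose records, and its first post-dose record is no worse than the pre-dose record but worse than the next, SAP 4.10.2 calls that first post-dose record both a TEAE and not a TEAE. The Case 2 answer conflicts with the section's own definition.

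This rests on applying the pairwise rule to each consecutive pair of linked records, which is the plain reading of the text but not the only one. The documents do not say how many such chains occurred, so the effect on the tables cannot be computed. The 4.3 to 4.8 points is the weight of any one patient in arms of this size, not an estimate of impact. No direction between arms can be claimed.

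**What to change.** Add to SAP 4.10.2, after Case 2:

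- Case 2 applies only to linked chains with no record before first dosing.
- In a chain with a pre-dose record, each post-dose record is compared with the last pre-dose record and is treatment-emergent only if its severity or seriousness is worse.
- Where several post-dose records qualify, only the worst counts as the TEAE. Mild (pre-dose), moderate, severe would then give one TEAE and not two.

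One consequence should be accepted knowingly: a return after dosing to the last pre-dose level, as in moderate, mild, moderate, would no longer be flagged. If the sponsor prefers to keep it, the text should say so.

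The cost is a few lines of SAP text and a small change to the derivation of the flag. No new data are needed, and no clinical management rule is affected.
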